4.2 Objectives

This multicentre RCT aims to investigate the clinical efficacy of SIGHT on post-stroke neglect when delivered by a therapist in tightly controlled within-hospital settings, whilst simultaneously determining the causes of differing responses to therapy between individuals. Our primary research aims are to:

(1) determine whether SIGHT in addition to TAU produces greater reduction in neglect than TAU alone (i.e., standard occupational therapy for neglect).

(2) determine whether benefits from SIGHT are still evident at the 12-week follow-up after the intervention ends.

(3) determine if therapy response is modified by: (a) lesion location; (b) left and right IPS functional connectivity; (c) left and right IPS structural connectivity; (d) perception-grasping dissociation; (e) stroke severity, (f) visual and/or (g) cognitive deficits.

Our testable hypotheses, generated by our early phase work and neuroimaging studies [16,19-20,26-27], are that:

(1) when added to treatment as usual (TAU), 30 minutes/day of SIGHT for 7 days (over a 10-day period) will produce greater reduction in neglect than TAU alone.

(2) patients with impaired IPS structure or function will benefit less from SIGHT.

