5.4.6 Protocol Treatment Discontinuation

In consenting to the trial, participants are consenting to trial treatments, trial follow-up and data collection. However, an individual participant may stop treatment early or be stopped early for any of the following reasons:

- A new diagnosis of a pathology or adverse event that impacts the participant's ability to take part in the trial or confounds response to SIGHT, e.g., cancer, upper limb fracture.
- Any change in the participant's condition that in the clinician's opinion justifies the discontinuation of treatment.
- Withdrawal of consent for treatment by the participant.
- Participant moves out of catchment area of clinical centre (acute or community).
- Death

As participation in the trial is entirely voluntary, the participant may choose to discontinue trial treatment at any time without penalty or loss of benefits to which they would otherwise be entitled. Although not obliged to give a reason for discontinuing their trial treatment, a reasonable effort should be made to establish this reason, whilst remaining fully respectful of the participant's rights.

Data collected up to the date of withdrawal will be retained and included in data analysis.

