5.6.2 Early Stopping of Follow-up

If a participant chooses to discontinue their trial treatment, they should continue to be followed up as closely as possible to the follow-up schedule defined in the protocol, providing they are willing. They should be encouraged and facilitated not to leave the whole trial, even though they no longer take the trial treatment. If, however, the participant exercises the view that they no longer wish to be followed up, this view must be respected and the participant withdrawn entirely from the trial. NCTU should be informed of the withdrawal using the appropriate SIGHT trial documentation as soon as possible. Deaths should also be reported as a withdrawal. Data already collected will be kept and included in analyses according to the intention-to-treat principle for all participants who stop follow up early.

Randomised participants who stop trial follow-up early will not be replaced. Recruitment will be monitored by DMEC and if recruitment is below expected due to drop-outs trial team may seek approvals to increase sample size.

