5.7 Sample Size

The efficacy study is powered to detect a significant change from baseline to T1 between the intervention and control groups for the primary outcome of the Star Cancellation sub-test of the BIT [43]. Our sample size calculation is directly informed by our published proof-ofconcept study [16] which found that the SIGHT+TAU group (N=10) had significantly greater neglect improvement on the BIT than the SHAM+TAU group (N=10; $F_{(1,18)}$ =6.7, p=0.018, partial n²_p=0.27; see Fig.1). Specifically, informed by this data we have assumed an effect of size of 0.6 (equivalent to partial n²_p=0.27 [16]). Stroke (and neglect) recovery takes place most rapidly over the first 7 days post-stroke and has been shown to decrease at around 3 months post-stroke [32]. Early after stroke, it has been reported that between 2-days and 9days post-stroke, 33% of patients with neglect significantly improve in the Star Cancellation Test (median Star Cancellation score at 2 days=31 and 9 days=47; cut-off=51; max=54), with 67% showing poor recovery (median Star Cancellation score at 2 days=26 and 9 days=35). The c-SIGHT feasibility trial data [17] shows that at 3-months post-stroke, 42% of neglect patients have recovered on the Star Cancellation Test (median score at 3 months=53) in line with a recent meta-analysis of 12 studies (N=262 patients, [85]). Thus, to accommodate the additional 10-15% natural recovery rate between 1-week and 3-months post-stroke, we reduced our effect size from 0.6 (estimated from PoC data at 3 months poststroke [16]) by 15% to 0.51, which with 90% power at the 5% level of significance using a two-sample t-test requires 206 participants (103 per group), including a 20% dropout. The effect size of 0.51 represents a difference of approximately 6.1 points on the Star Cancellation sub-test assuming a SD of approximately 12 obtained from our previous studies [16,17]. As the proposed trial compares SIGHT+TAU and TAU alone we expect our effect size to be larger than the one found in our proof-of-concept study [16]. Natural recovery is further accounted for in the design as some neglect improvement will occur in both experimental and control groups in a similar way since they are balanced for neglect severity - a strong predictor of stroke recovery [38; see randomisation strata]. The intervention effect is additional to natural recovery. The 20% dropout rate is based on our feasibility trials in post-stroke neglect with an average of 17.5% dropout in experimental arm at the 12-week post-intervention follow-up (15% [17] and 20% [56]).

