5.10.4 Statistical Methods

5.10.4.1 Outcomes

Analysis will be conducted according to random group allocation (intention-to-treat principle). Baseline characteristics of the participants will be summarised using descriptive statistics by groups, n (%) for binary and categorical variables and mean (SD)/median (QIR) for continuous variables. Flow of the participants through the trial will be reported using the CONSORT flow diagram. A descriptive summary of the treatment received as well as adherence and fidelity measures will be given. A full statistical analysis plan will be pre-registered prior to completion of data collection, thus adhering to open and replicable research practices.

The clinical efficacy analysis will compare continuous outcome variables between treatment groups, using a general linear model at each time-point separately adjusting for stratification factors. To account for potential TAU variability across sites, clinical centre will be used as a co-variate. The effect of treatment will be summarised using the adjusted mean difference and 95% confidence interval. Dependent variables will include: Star Cancellation score (primary), CBS KF-NAP score, line bisection error and OCS Hearts overall, ego- and all centric scores and SIS scores in each domain.

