Missing data will be excluded in the primary analysis. However, the sensitivity of the missing data on the outcomes will be assessed by carrying out multiple imputation assuming that the data is missing at random. If we have reason to believe that the data is not missing at random, then pattern mixture models will be used to assess sensitivity.

Adverse events will be recorded including falls and classified in terms of seriousness and relatedness and a between group analysis will be conducted for those related to the study and overall to examine if therapy has an impact on number of falls.

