5.10.4.5 Missing Data

Missing data will be excluded in the primary analysis. However, the sensitivity of the missing data on the outcomes will be assessed by carrying out multiple imputation assuming that the data is missing at random. If we have reason to believe that the data is not missing at random, then pattern mixture models will be used to assess sensitivity.

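### The 12-week comparison is fitted to T2 completers alone and ignores the T1 scores of participants lost in between, and those lost before T1 enter no primary efficacy model

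*Protocol*

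**What the plan says.** Two sets of statements in the protocol bear on who is analysed.

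- **Inclusion of early stoppers.** Section 5.4.6, on those who stop treatment: "Data collected up to the date of withdrawal will be retained and included in data analysis". Section 5.6.2, on those who stop follow-up: "Data already collected will be kept and included in analyses according to the intention-to-treat principle for all participants who stop follow up early". Section 5.6.2 also reports deaths as withdrawals.
- **The efficacy analysis.** Section 5.10.4.1 compares continuous outcomes "using a general linear model at each time-point separately adjusting for stratification factors", and adds: "Missing data will be excluded in the primary analysis". Section 5.10.4.5 repeats that rule and provides a sensitivity analysis in which "the sensitivity of the missing data on the outcomes will be assessed by carrying out multiple imputation assuming that the data is missing at random", with pattern mixture models if the data are thought not to be missing at random.

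The powered comparison is at T1: section 5.7 describes a study "powered to detect a significant change from baseline to T1 between the intervention and control groups for the primary outcome". The 12-week question is nevertheless listed in section 4.2 among the primary research aims: "determine whether benefits from SIGHT are still evident at the 12-week follow-up after the intervention ends".

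**The concern.** With one model per visit and missing values excluded, the T2 model sees only participants with a T2 score. For anyone lost between T1 and T2, the database holds a T1 score taken after treatment on the same scale, and probably the best available predictor of the missing value. The stated rule does not use it. Apart from what baseline and the stratification factors explain, the T2 comparison is then sound only if loss is unrelated to how the patient was doing at T1, or related to it in much the same way in both arms.

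Participants lost before T1 appear in the baseline summaries and the participant flow but in no primary efficacy model. That sits badly with the wording in 5.6.2, which covers all who stop follow-up early.

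At stake are the precision and possible bias of the estimate that answers whether benefit persists at 12 weeks.

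**Working it through.** **Inputs.** From section 5.7: effect size 0.51, SD about 12, difference about 6.1 points, 90% power, 5% level (taken as two-sided), 20% dropout, 103 per arm; the dropout figure rests on 12-week rates of 15% and 20% (mean 17.5%). From section 5.12.2: T1 completeness is green above 90%. The correlations and dropout mechanisms are not in the protocol and are assumed below.

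**1. The plan's own figure.** A two-sample t-test with effect 0.51 needs 81.8, so 82 per arm. 82/(1 − 0.20) = 102.5, so 103 per arm and 206 in total. 0.51 × 12 = 6.12. The sample size reproduces.

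**2. How many T1 scores the T2 model ignores.** With monotone loss, the share with T1 but no T2 is T2 loss minus T1 loss.

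| Missing at T1 | T2 loss 20% | T2 loss 17.5% |
|---|---|---|
| 0% | 20% (41 patients) | 17.5% (36) |
| 5% | 15% (31) | 12.5% (26) |
| 10% | 10% (21) | 7.5% (15) |
| all losses before T1 | 0% | 0% |

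The protocol does not split losses between T1 and T2.

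**3. Precision.** For a T2 arm mean under monotone loss, the joint likelihood variance is

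σ²[(1 − ρ²)/n₂ + ρ²/n₁],

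against σ²/n₂ for T2 completers alone. Take n₂ = 103 × 0.8 = 82.4.

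- T1 complete (n₁ = 103): the variance ratio is 1 − 0.2ρ². At ρ = 0.5 it is 0.950 (5% lower) and at ρ = 0.7 it is 0.902 (9.8% lower). Effective n per arm rises from 82.4 to 86.7 and 91.4. Power at effect 0.51 rises from 90.2% to 91.6% and 92.9%.
- 10% missing at T1 (n₁ = 92.7): the ratio is 1 − ρ²/9, so the gain is 2.8% and 5.4%.
- With baseline in the model, ρ is the partial correlation. Assuming T0–T1 0.6, T1–T2 0.75 and T0–T2 0.5, it is (0.75 − 0.6 × 0.5)/√(0.64 × 0.75) = 0.65, and 1 − 0.2 × 0.65² = 0.916, about 8% lower. Simulations with these correlations gave 5–10%.

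**4. Bias when T2 loss depends on the T1 score.**

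- *Poor T1 scorers leave SIGHT only* (20% missing in each arm, log-odds 1 per SD, no baseline adjustment): the 12-week difference is overstated by 1.04 points at ρ = 0.5 and 1.45 at ρ = 0.7. Both equal 12 × ρ × 0.173, where 0.173 SD is the upward shift in mean T1 score among those retained.
- *Poor T1 scorers leave TAU only* (baseline-adjusted, correlations as above, about 18–20% loss, log-odds 0.1 per point or 1.2 per SD, 2,500 to 4,000 simulated trials): the estimate is 4.9–5.1 for a true 6.1. With no true effect it is −1.0 to −1.25, and type I error is about 9–12%.
- *Same dependence in both arms*: the estimate is 5.7–5.8 for a true 6.1, with no bias under the null.
- *Loss unrelated to outcome*: no bias.

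The joint estimate was unbiased throughout, as it should be for data generated as missing at random from a multivariate normal model.

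**5. Check on the type I error.** The baseline-adjusted residual SD is 12 × √(1 − 0.5²) = 10.39, so SE = 10.39 × √(2/82.4) = 1.62. A null bias of 1.0 is 0.62 SE: Φ(−1.34) + Φ(−2.58) = 0.090 + 0.005 = 9.5%. A bias of 1.25 is 0.77 SE: 0.117 + 0.003 = 12%. Nearly all of the excess lies on one side: against SIGHT when poor scorers leave TAU, in its favour when they leave SIGHT.

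**The case against.** A reader might infer that the protocol defines two contradictory analysis populations. It does not, for most of those affected. Sections 5.4.6 and 5.6.2 speak of data already collected, while 5.10.4.1 and 5.10.4.5 exclude values that were never obtained. A participant seen at T1 and lost before T2 has a T1 score, and that score enters the T1 model, which is the primary comparison. This part of the objection stands. What remains is the group lost before T1, and the fact that the inclusion wording does not say at which visit the data count.

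A reader might also infer that a fifth of patients' T1 data are thrown away. A fifth is the ceiling, reached only if every T2 loss has a T1 score, and those scores are set aside only in the T2 estimate.

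Multiple imputation and pattern mixture models are already planned, and imputation that includes T1 deals with the same mechanism as a joint model. That is a fair point. But they are sensitivity analyses, the protocol does not say whether T1 is among the imputation variables, and the main T2 estimate stays the completers-only one. The imputation variables could be left to the statistical analysis plan. The main rule is not left open, because the protocol fixes it twice.

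Finally, the larger bias figures need strong T1-dependent loss in one arm only, and nothing in the protocol shows that this will occur. The unequal attrition in the feasibility trial came from dislike of a sham that this trial has dropped. At half the slope in the TAU-only case the null bias is about −0.5 and the error rate about 6%. This stands too: the bias is a possibility to guard against, not a forecast.

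**Conclusion.** The point holds for the 12-week estimate and is moderate in size. The stated rule leaves out the T1 scores of participants lost between T1 and T2: at most about 20% of patients, 7.5–10% if 10% already lack T1, and none if all losses come earlier. The cost in variance is about 5–10% when T1 is nearly complete and the T1–T2 correlation is 0.5 to 0.7, and less otherwise. Under assumed one-arm T1-dependent loss the bias is about 1 point against 6.1, its sign set by the arm affected, with type I error around 9–12%. Under equal dependence it is 0.3–0.4 points.

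It should not be read as a fault in the primary result. The T1 contrast and the total of 206 are essentially unaffected. Separately, participants lost before T1 enter no primary efficacy model, and the inclusion wording in 5.4.6 and 5.6.2 should be brought into line with that.

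**What to change.** 1. **Section 5.10.4.1.** For outcomes measured at T0, T1 and T2, take the 12-week estimate from one likelihood-based repeated-measures model per outcome, with treatment-by-visit terms, the stratification factors, unstructured covariance and all randomised participants with at least one post-baseline value. The T1 contrast (primary) can be read from the same model. Alternatively, keep the per-visit model and take the main T2 estimate from multiple imputation that includes T1.
2. **Sections 5.10.4.1 and 5.10.4.5.** Replace the exclusion rule with wording that matches the chosen model. Keep multiple imputation and pattern mixture models as sensitivity analyses, and name T1 as an imputation variable for T2.
3. **Sections 5.4.6 and 5.6.2.** State who is analysed at each visit. Participants with no post-baseline value stay out of the repeated-measures model too, so the text should say so and say where their data are used.
4. **Stroke Impact Scale.** It is collected at T2 only and keeps a single-visit model.

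The cost is a wording change and slightly more analysis work, with no new data and no change in sample size. The model adds a covariance assumption. It also projects T2 scores under missing at random for all losses, including deaths, as the planned imputation already does.

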5.6.3 Participant Transfers

If a participant moves from a consenting acute hospital setting to a linked community hospital setting making continued trial procedures at their consenting acute centre not possible, every effort should be made for them to continue the trial at the new location. Established communication and links between delegated sites will ensure patients flowing from acute to community will continue to receive the trial as expected through the duration of their participation. However, should a patient move from a consenting acute hospital to a site not participating in SIGHT, the patient will be withdrawn.

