5.1.1 Study Setting

Participant recruitment will be from stroke centres in NHS trusts, within wards and community hospitals across the UK.

The trial has been designed to allow T1 and T2 assessments to be delivered where the patients are discharged to (e.g., own homes) avoiding additional travel to hospital settings and thus reducing the burden on participants. Baseline assessments and interventions are delivered while the patient is within hospital settings to maximise controlled conditions and avoid additional travel to hospitals or transfer by ambulance for MRI.

Both sites with and without MRI can participate as only a subsample of patients (80) are required to meet the target for the MRI mechanistic sub study.

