5.10.3 Non-Adherence and Non-Retention

Reasons for non-adherence will be recorded where possible. Primary outcome data will be recorded for all those randomised.

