6.1 Research Ethics and Health Research Authority Approval

Before initiation of the trial at any clinical site, the protocol, all informed consent forms and any material to be given to the prospective participant will be submitted to the relevant REC and to HRA for approval. Any subsequent amendments to these documents will be submitted for further approval.

The rights of the participant to refuse to participate in the trial without giving a reason must be respected. After the participant has entered the trial, the clinician remains free to give alternative treatment to that specified in the protocol, at any stage, if s/he feels it to be in the best interest of the participant. The reasons for doing so must be recorded. After randomisation the participant must remain within the trial for the purpose of follow up and data analysis according to the treatment option to which they have been allocated. However, the participant remains free to change their mind at any time about the protocol treatment and follow-up without giving a reason and without prejudicing their further treatment.

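### The transfer rule withdraws patients because the receiving hospital is not a trial site, against the protocol's own follow-up provisions, and so gives up T1 and T2 data that could be obtained

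*Protocol*

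**What the plan says.** Section 5.6.3 first asks that patients moving to a linked community hospital carry on in the trial there. It then sets the contrary case: "should a patient move from a consenting acute hospital to a site not participating in SIGHT, the patient will be withdrawn". It says nothing about T1 or T2 for these patients.

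Other sections point the other way:

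- Section 5.4.6 lists a move out of the centre's catchment among the reasons for stopping trial treatment.
- Sections 5.4.2.1 and 5.6.2 keep participants who stop treatment in follow-up if they are willing. In 5.6.2, complete withdrawal follows the participant's own wish, and deaths are also reported as withdrawals.
- Sections 5.6.1.5 and 5.6.1.6 give all participants a blinded-assessor visit at T1 (Day 11, up to 5 days later) and T2 (12 weeks, plus or minus 10 days).
- Section 5.10.3: "Primary outcome data will be recorded for all those randomised".
- Section 6.1: "After randomisation the participant must remain within the trial for the purpose of follow up and data analysis according to the treatment option" (that is, as allocated).

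Off-site assessment is part of the design. Section 5.1.1 allows T1 and T2 at the place of discharge, such as the patient's home. Section 5.1.2.2 requires sites to have assessors who can work outside the recruiting hospital. Section 5.8.2 says that home visits are funded.

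**The concern.** A transfer may affect whether remaining SIGHT sessions can be given. It does not by itself stop a blinded assessor from administering the Star Cancellation test. Arm A patients have no trial sessions to lose, so for them the receiving hospital's status matters only for assessment and for recording usual care.

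The rule therefore ends outcome collection on an administrative ground, not at the participant's wish. A patient sent home is visited; one moved to another hospital is dropped. Those who still need inpatient care probably differ in severity from those who go home, so the loss is unlikely to be random.

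The primary analysis excludes missing data (Sections 5.10.4.1 and 5.10.4.5). A patient withdrawn before T1 contributes nothing to it. A patient withdrawn after T1 still loses T2, which the second aim in Section 4.2 needs.

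**Working it through.** **1. What the rule means.** Section 5.6.3 contrasts withdrawal with continuing the trial at a linked hospital and makes no follow-up provision. The section before it uses withdrawal in the sense of leaving the trial altogether. Whole-trial withdrawal is the natural reading, though 5.6.3 does not spell it out.

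**2. The sections side by side, for a patient who moves to a non-participating hospital.**

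| Section | Consequence |
|---|---|
| 5.6.3 | Withdrawn |
| 5.4.6 | Treatment may stop |
| 5.4.2.1, 5.6.2 | After stopping treatment, follow-up continues if the participant is willing |
| 5.6.1.5, 5.6.1.6 | T1 and T2 visits take place |
| 5.10.3, 6.1 | Primary outcome recorded; participant stays for follow-up |

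A site cannot follow the first row together with the others.

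**3. Whether the entry criteria close the gap.** Section 5.3.1.3 excludes patients expected to go home, or to a hospital outside the participating hub, within 7 days. T1 runs from Day 11 to Day 16. Even counting the 7 days from randomisation, 11 − 7 = 4 to 16 − 7 = 9 days before T1 are not covered, nor is the rest of the period to week 12. Entry is at least 7 days after stroke, so T1 falls at 7 + 11 = day 18 post-stroke or later. Section 5.8.1 gives an average stay of 21 days for neglect patients. Moves before T1 are foreseeable, but that figure is a length of stay, not a transfer rate.

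**4. The planned sample size.** Section 5.7 specifies "90% power at the 5% level of significance using a two-sample t-test", an effect size of 0.51 and 20% dropout. It adds: "The effect size of 0.51 represents a difference of approximately 6.1 points on the Star Cancellation sub-test", with an SD of about 12 (0.51 × 12 = 6.12). Sidedness is not stated; two-sided is assumed.

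- Two-sample t-test, d = 0.51, two-sided 5%, 90% power: 81.8, so 82 per group.
- Dropout: 82 / (1 − 0.20) = 102.5, so 103 per group and 206 in total. This reproduces the plan exactly.

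**5. Power by total T1 loss L.** Analysed per group = 103 × (1 − L). Number to randomise for 90% power = 2 × (82 / (1 − L), rounded up).

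| Total T1 loss | Analysed per group | Power | N for 90% |
|---|---|---|---|
| 10% | 92.7 | 93.2% | 184 |
| 15% | 87.55 | 91.9% | 194 |
| 20% (planned) | 82.4 | 90.2% | 206 |
| 25% | 77.25 | 88.3% | 220 |
| 30% | 72.1 | 86.0% | 236 |

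The protocol does not give the share of L that transfers would cause. The 25% and 30% rows are assumptions that show the scale.

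**The case against.** The case against has several parts.

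- **Exposure is limited.** Moves expected within 7 days are excluded, at least 8 community centres are planned, linked transfers continue, and patients discharged home are followed up. This stands, and it narrows the affected group. It does not help a patient whose receiving hospital is outside the trial.
- **Access may be the reason for the rule.** Sections 5.1.2 and 6.3 require local confirmation at each NHS site, and no section addresses an assessor visiting an inpatient at a non-participating hospital. This stands. A reader might infer that T1 and T2 can be done anywhere; Section 5.1.1 does not go that far. Access may sometimes be refused, but that is no reason not to seek it.
- **The general statements cannot be literal.** Section 5.10.3 sits under non-adherence, Section 6.1 goes on to let participants change their mind, and Section 5.6.2 allows withdrawal. Intention-to-treat here means analysis as allocated, so a missing T1 does not in itself breach it. This weakens the weight of 5.10.3 and 6.1, but not the conflict with 5.4.6 and 5.6.2.
- **A power loss is not shown.** The 20% allowance comes from 12-week dropout in the experimental arms of feasibility trials, whereas the primary endpoint is at Day 11 to 16, and Section 5.12.2 sets its green threshold for T1 completeness above 90%. If other T1 loss were 10% and transfers added 10 points, the total would be the planned 20% and power 90.2%. This stands.
- **Bias between arms.** A reader might infer that staff hold SIGHT patients back until sessions finish, so that more usual-care patients are withdrawn. The documents do not support this. The rule is the same for both arms, allocation is notified to those delivering therapy and withheld from recruiting staff and assessors (Sections 4.3 and 5.9.2), and nothing says that ward staff know the arm or time transfers by it. The shift in the estimate would be roughly the extra share lost in one arm times the outcome gap between lost and retained patients. For example, 0.10 × 0.5 SD × 12 = 0.6 points, but both inputs are assumed. Adjustment for stratification factors could absorb part of it, and multiple imputation and, if needed, pattern-mixture sensitivity analyses are planned.

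**Conclusion.** The inconsistency is real and should be corrected. Section 5.6.3 makes the receiving hospital's site status a ground for withdrawal, while the rest of the protocol treats a move as affecting treatment and keeps follow-up open unless the participant declines. Followed as written, the rule loses T1 and T2 data that could often be collected, and any patient withdrawn before T1 leaves the primary complete-case analysis.

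The conclusion rests on reading withdrawal as withdrawal from the whole trial, which is natural but not explicit. Its numerical effect cannot be fixed from the protocol. Power is about 88% or 86% if total T1 loss reaches 25% or 30%, and the stated 90% holds if loss stays within 20%. The documents do not show that power will fall below plan or that loss will differ by arm; both remain possible. The sample size of 206 is not in dispute.

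**What to change.** Reconcile Section 5.6.3 with Sections 5.4.6, 5.6.2, 5.10.3 and 6.1:

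- Record a transfer to a non-participating hospital as its own event, separate from withdrawal from follow-up.
- Have the blinded assessor seek T1 and T2 at the new location, or after discharge if that falls within the visit window, unless the participant or consultee declines or access is refused. Record the reason when a visit is not done.
- Analyse these participants as randomised.
- Report the number and timing of transfers by arm, relative to T1 and T2, so that any imbalance is visible.

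What happens to remaining intervention sessions after a transfer is for the sponsor to reconcile across the same sections; this point concerns outcome collection only.

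The cost is a wording amendment, some assessor travel, and access permission at receiving hospitals, which may not always be granted.
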